2.1 Indication for Use

The EndoRotor[®] is intended for use in endoscopic procedures by a trained gastroenterologist to resect and remove tissue, not intended for biopsy, of the gastrointestinal (GI) system including post-endoscopic mucosal resection (EMR) tissue persistence with a scarred base and residual tissue from the peripheral margins following EMR. The EndoRotor[®] System resects and removes mucosal tissue simultaneously through a catheter inserted into the working channel of a flexible endoscope. The EndoRotor[®] System will be used for removal of mucosal/sub-mucosal

tissue in the colon within the 510(k) clearance indications and according to the Instructions for Use.

2.2 Contraindications

The EndoRotor® should not be used for the primary resection of lesions or for tissues intended for biopsy.

2.3 Device Use in Clinical Study

Devices will be used in the study whenever an Investigator decides to use the EndoRotor® System for standard of care removal of mucosal/sub-mucosal tissue in the colon.

3.0 POST-MARKET STUDY PLAN

3.1 Study Objective

This study is being conducted as a post-market 510(k) study to collect data in support of the safety and performance of the Interscope EndoRotor[®] Endoscopic Mucosal Resection System. The study will demonstrate that EndoRotor[®] resections are safe and effective and support market adoption efforts.

3.1.1 Study Design

This study has been designed as a prospective, non-randomized, multi-center, observational study for the treatment of subjects with the need for resection of recurrent, flat or sessile dysplastic/adenomatous rectal/colonic mucosa where EndoRotor is the primary resection modality.

3.1.2 Enrollment

Total enrollment is 60 evaluable subjects at up to 15 clinical sites in the United States and Europe. Each site may enroll a minimum of one (1) subject and a maximum of 8 subjects until a maximum of 60 evaluable subjects are enrolled.

3.1.3 Study Population

Adult (>18 years to \leq 85 years) subjects who have at least one recurrent flat or sessile rectal/colon mucosal polyp up to 6 cm in diameter and/or length.

3.2 Study Duration & Follow-Up

It is anticipated that the study will begin enrollment in June 2019. Enrollment is expected to continue until December 2019. Study subjects shall return for clinic visits in 90 days (+/- 14 days) post-procedure; data from these visits shall be collected. Primary and other endpoints will be assessed. All subjects will be treated per this protocol, the Instructions for Use, and as per standard of care, as indicated. The last follow-up visit is expected to be completed by March 2020 at the last subject's 90-day (+/- 14 days) follow-up visit. The study is complete following the collection of all study data and all final site visits have been completed in June 2020.

4.0 STUDY ENDPOINTS AND SUBJECT POPULATION

4.1 Primary Endpoints

Primary Effectiveness Endpoint (Performance):

Technical Success, defined as the ability of the EndoRotor device to resect recurrent flat or sessile colorectal lesions without concomitant use of other resection modalities for mucosectomy and no definitely or probably device-related serious adverse events (SAEs) throughout the 90-day follow-up period.

Primary Safety Endpoint:

Assessment of Serious Adverse Events (incidence, relationship to device and severity) at index procedure and at 90 days, post-procedure.

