4.2 Secondary Endpoints

The following is a list of other secondary endpoints to be explored:

- 1. Completeness, in percentage, of resection based on endoscopy film and/or photographs in addition to diagnostic assessment of specimen by the independent pathologist.
- 2. Presence of colon stenosis based on endoscopy film and/or photographs.
- 3. Rate of persistence of disease at the location of resection at 90 days.
- 4. Histologic assessment of the diagnostic value of the collected specimens.

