5.7 Index Procedure

All patients will receive the EndoRotor® treatment following the technique described by Interscope's Instructions for Use.

The mucosal resections are performed during standard flexible colonoscopy procedures. All medications given, pre- and post-procedure precautions and follow-up assessments are part of routine standard of care. This protocol concerns itself with the actual removal of the mucosal lesion once the abnormal area is identified using the colonoscope.

- Patients will be prepped in the usual manner for lower GI endoscopy prior to their interventional visit.
- The procedures will be performed with either Propofol sedation or under general anesthesia.
- When a mucosal lesion is found, the EndoRotor® system will be prepared by attaching the EndoRotor® catheter, foot pedal and the calibrated suction to the Control Unit, ensuring there is a filter in the collection unit (specimen trap), and then priming the catheter with 0.9% normal saline.
- Lesions will be injected using saline solution with dye such as Indigo carmine or Methylene Blue. Indelible ink (such as SPOT) will be injected into the region of the resection to identify the site after resection.
- The EndoRotor® catheter will be inserted through the working channel of the endoscope until it is in proper cutting position with the cutting surface oriented towards the mucosal lesion and the catheter no more than 3cm out of the scope. The physician will turn the motor on by depressing the blue pedal and engage cutting by holding the orange pedal for as long as he/she wishes to cut tissue.
- Cutting should be performed while moving the EndoRotor® catheter. The endoscopist will take care to not keep the suction activated when he/she is not intending to cut mucosa and when stopped for more than 1 second while apposed to tissue to not risk creating a perforation.
- Various techniques can be used to remove the lesion. Recurrent, flat or sessile lesions will be attempted to be removed entirely with the EndoRotor® with no other treatment modalities. The physician will utilize the recommended technique appropriate to the lesion until there is no longer visible evidence of mucosal lesion. The intent of the protocol is to complete lesion resection using the EndoRotor as the only treatment modality. However, should it prove not feasible to complete the resection with the EndoRotor, the investigator may convert to the use of an alternative resection modality.

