- For synchronous lesion interventions, respective lesion specimens should be isolated and separately collected to avoid confounding results.
- APC or similar techniques used for hemostasis on a resected lesion is not considered an alternative resection modality.
- Treat with EndoRotor, assess percentage of tissue removed with EndoRotor followed by photograph from region at equidistant location.
- Photo-document the region following EndoRotor treatment.
- If the complete lesion cannot be removed in a single treatment visit, a second visit can be scheduled to complete the removal in advance of the 90 day visit.

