8.2 Analysis Populations

Two analysis populations are defined for this protocol, Intent to Treat and Per Protocol.

Intent to Treat Population: All subjects in whom the EndoRotor was used for any resection of a lesion. This includes those subjects that were either treated with the EndoRotor alone or with another adjunctive modality.

Per Protocol (PP): Subset of the Intent to Treat population including those subjects who had complete lesion resection with the EndoRotor alone without any adjunctive modality resection, did not have inclusion/exclusion protocol deviations and completed the 90 day follow up visit. The effectiveness analyses will be conducted on the per protocol population.

Safety Population: Defined as all subjects who were treated with the device.

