8.4 Primary Endpoint Analysis

The primary analysis will be completed on the Per Protocol population and will consist of all evaluable subjects enrolled in the study who have documented recurrent flat or sessile colorectal lesions up to 6 cm in diameter and/or length and are treated with the Interscope device without adjunctive modality. The analysis will be conducted on the percent of lesions with persistent disease. The primary endpoint is:

Technical Success, defined as the ability of the EndoRotor device to resect recurrent flat or sessile colorectal lesions without concomitant use of other resection modalities for mucosectomy and no definitely and probably device-related serious adverse events (SAEs) throughout the 90-day follow-up period.

This analysis population will be used to describe the primary effectiveness and the secondary endpoints. A confidence interval for the successful removal of all lesions will be calculated by Clopper-Pearson exact methods⁶ if all subjects are treated for one lesion. In the event that one or more subjects are treated for multiple lesions, then a generalized estimating equation with a logistic link function will be used to estimate the 95% confidence interval of the success rate.

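### Technical Success never states that the lesion must be completely removed, and the Per Protocol rule excludes incomplete or converted resections instead of counting them as failures

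*Combined protocol and SAP*

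**What the plan says.** The definition in 4.1, repeated in the protocol summary and in 8.4, asks for "the ability of the EndoRotor device to resect recurrent flat or sessile colorectal lesions without concomitant use of other resection modalities" and for no definitely or probably device-related SAE over the 90-day follow-up. It does not say that removal must be complete, and it does not define when another modality counts as concomitant.

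Completeness appears in four other places:

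- **4.2** lists it as a separate secondary endpoint: "Completeness, in percentage, of resection based on endoscopy film and/or photographs". No cut-off links it to Technical Success.
- **5.7** has the operator continue "until there is no longer visible evidence of mucosal lesion". It also permits conversion to another modality if completion with the device is not feasible. If one session is not enough, "a second visit can be scheduled to complete the removal in advance of the 90 day visit". Neither 5.7 nor footnote 7 of Appendix 1 says which modality is used at that visit or how the subject is scored.
- **8.2** makes "complete lesion resection with the EndoRotor alone without any adjunctive modality resection" a condition of belonging to the Per Protocol set, and adds: "The effectiveness analyses will be conducted on the per protocol population".
- **8.4** describes the interval in terms that imply completeness: "A confidence interval for the successful removal of all lesions will be calculated by Clopper-Pearson exact" methods. The same section also says that the analysis concerns the percentage of lesions with persistent disease, which is a different quantity.

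**The concern.** Leaving lesion behind, or needing another technique to finish, is the direct way in which a resection device falls short. Under this plan such a case is scored as a failure nowhere. The definition does not name it, and the population rule removes it before the rate is calculated.

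The secondary endpoint does not recover the information. Section 8.4 uses the same Per Protocol set for the secondary endpoints, so completeness of resection will be summarised only in subjects selected for having a complete resection.

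The study is justified in 7.2 by comparison with other devices. Section 1.3.2 reports completeness of 73-100% in the literature and names completeness and recurrence as the most commonly cited outcomes. A rate that cannot register residual tissue cannot be set beside those figures.

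**Working it through.** **The plan's own figure (8.8).** Inputs: N = 60, success rate 0.85, 95% exact interval, stated half width 0.0972, stated limits 0.782 to 0.967.

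- With x = 0.85 × 60 = 51, the Clopper-Pearson limits are the 0.025 quantile of Beta(x, n − x + 1) = Beta(51, 10) and the 0.975 quantile of Beta(x + 1, n − x) = Beta(52, 9).
- Result: 0.734 to 0.929, half width 0.0974. This agrees with the stated half width to within 0.0002 and meets the 0.10 target.
- The stated limits are not reproduced. That is a separate error and does not bear on this point.

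**How each kind of case is treated.**

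| Case | Definition in 4.1 | Per Protocol set (8.2) | Effect on the planned rate |
|---|---|---|---|
| Complete, EndoRotor alone, no qualifying SAE | success | in | success |
| Complete, EndoRotor alone, qualifying SAE | failure | in | failure |
| Converted in the same session | failure | out | none |
| Incomplete, not converted | not settled | out | none |
| Finished later by another technique | not settled | out | none |
| Finished at a second EndoRotor session | not settled | not stated | not stated |

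Even the converted case, which 4.1 clearly makes a failure, cannot lower the reported rate.

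**Size.** The documents give no rate of incomplete or converted resections, so the counts are assumptions. Take 60 treated subjects, all with a 90-day visit and no eligibility deviation, of whom 51 are true successes. Let k of the 9 failures be resection failures and 9 − k be complete resections with a qualifying SAE. Then

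all-treated rate = 51/60 = 85.0%; Per Protocol rate = 51/(60 − k).

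| k | Per Protocol rate | Exact 95% CI |
|---|---|---|
| 0 | 51/60 = 85.0% | 0.734 to 0.929 |
| 3 | 51/57 = 89.5% | 0.785 to 0.960 |
| 6 | 51/54 = 94.4% | 0.846 to 0.988 |
| 9 | 51/51 = 100% | 0.930 to 1 |

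For k = 9 the lower limit is 0.025^(1/51) = 0.930, just above the upper limit of 0.929 for the all-treated rate.

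**Consistency with 8.8.** An expected rate of 0.85 means 9 failures in 60. Within the Per Protocol set, all 9 would have to be subjects with a definitely or probably device-related SAE. This suggests, without proving it, that resection failures were meant to count.

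**The case against.** A reader of 4.1 alone might infer that an abandoned partial resection, or one finished later by another technique, is reported as a success. On that reading, 3 to 6 such subjects would lift 51/60 to 54/60 = 90% or 57/60 = 95%. The documents do not support this. Section 8.4 puts the interval on removal of all lesions, and 5.7 states the aim of clearing the lesion with EndoRotor as the only modality. The Per Protocol condition in 8.2 is not limited to same-session use, so both kinds of case fall outside the set. No effectiveness analysis of all treated subjects is planned in which they could enter the numerator. They are dropped, not counted as successes.

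It can also be said that the study is single-arm, post-market and primarily descriptive, with no hypothesis test, so no formal decision turns on the rate. That is true, but the rate is still the primary result and will be read as the device's ability to do the job.

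Finally, the Per Protocol condition could be taken to supply the completeness that 4.1 omits. It supplies it as an entry condition. That settles who is analysed and leaves unanswered how often complete removal was achieved.

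**Conclusion.** The point holds in this form: completeness and device-alone resection select the analysis set when they should be part of the outcome, and the definition itself is silent on both the degree of removal and the window for other modalities. The planned rate is pushed towards 100% by construction. If all 9 failures in 60 were resection failures, 85% would be reported as 100%; if 3 or 6 were, as 89.5% or 94.4%. These counts are assumptions. If every failure were an SAE after a complete EndoRotor-alone resection, there would be no distortion.

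The direction does not depend on the counts: excluding resection failures can only raise the rate or leave it unchanged. The unscored second visit is a further gap whose direction cannot be judged from the documents.

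**What to change.** 1. **Definition (4.1, 8.4 and the protocol summary).** Success requires all three of the following:
   - complete removal of every target lesion by EndoRotor alone, judged by the standard already in 5.7 (no visible lesion);
   - no other resection modality, and no ablation of residual lesion, at that site up to the 90-day visit. Keep the provision in 5.7 that APC or similar techniques used for hemostasis do not count;
   - no definitely or probably device-related SAE through 90 days.
2. **Second session.** State whether a lesion cleared at a second EndoRotor session before day 90 is a success.
3. **Population (8.2 and 8.4).** Make the primary analysis population all subjects treated with the device. Score incomplete, converted or otherwise-completed cases as failures, and keep Per Protocol as supportive. Rewording the endpoint without this step would change nothing, because the cases would still be excluded. Say also whether attempts aborted without tissue resection belong to this population; 5.3 follows them only to discharge, and the present Intent to Treat wording leaves them out.
4. **Missing 90-day visits.** The Per Protocol rule now removes these subjects and 8.9 drops missing outcomes. With the 10% loss anticipated in 5.4, that is up to 6 of 60, so an all-treated analysis needs a stated rule for them.

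**Cost.** Wording changes in the sections named, and a check that the case report form records the percentage removed, which 5.7 already has the operator assess, and any later treatment of the site. The item in 5.7.1 asks only whether the attempted resection was achieved. The reported success rate will be lower than under the Per Protocol rule.

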5.7.1 Index Procedure Details

Refer to the Instructions for Use for a description of the procedure. The following data will be collected on all subjects during the index procedure and prior to discharge on the Index Procedure case report form:

- Summary of symptoms from physical examination
- Endoscopic imaging study
- The EndoRotor® achieved the attempted resection of the targeted lesion(s).
- The EndoRotor® pathological specimens were able to be interpreted by GI pathologists and enabled the rendering of clinical diagnoses.
- The total number of recurrent lesions treated with the EndoRotor.
- Time from scope insertion to scope removal.
- EndoRotor time from resection start to resection end.
- Adverse event assessment and treatment (i.e. delayed bleeding, presence of perforations). Note: Typical and routine steps (endoscopic clipping/mucosal apposition) will be taken to close perforations if they are discovered.
- Ease of use and overall satisfaction with the EndoRotor® System.
- Identification of technical difficulties and device malfunction, if any.
- Photographs post-EndoRotor treatment.

Current standard of care does not guarantee pathology in recurrent lesion procedures due to the difficulty to remove they often are treated with avulsion or Argon Plasma Coagulation. Since the EndoRotor retrieves specimen it can be sent for histopathological review. Although the EndoRotor is not intended for biopsy in this study pathologist will also be able to evaluate specimen that would normally be ablated. Resected tissue collected in the Specimen Trap will be placed in 10% Formalin and sent to the resident pathologist for histological evaluation. The

following steps will be taken for the review and interpretation of the specimens from the Specimen Trap following the procedure:

- 1. The resident pathologist shall be responsible for the preparation of the histology slides and the review and interpretation of the slides per hospital standard operating procedures.
- 2. The prepared specimen will be de-identified per hospital procedure and shipped by courier to an independent pathologist.
- 3. An independent pathologist selected by the Sponsor will prepare histology slides to assess the quality of the specimens.
- 4. The independent pathologist will document his/her assessment of the quality of the specimens.

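### The endpoint and the primary analysis set define EndoRotor-only treatment differently, so a subject ablated after full EndoRotor resection is a success or is left out, and is never explicitly a failure

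*Combined protocol and SAP*

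**What the plan says.** Four places in the combined protocol and SAP describe EndoRotor-only treatment, and the scope is not the same in each.

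- **Endpoint (synopsis and 4.1).** The modality condition is "without concomitant use of other resection modalities for mucosectomy". Section 8.4 restates it with the same qualifier: "without concomitant use of other resection modalities for mucosectomy and no definitely and probably device-related serious adverse events".
- **Primary analysis set (8.4).** Subjects must be those who "are treated with the Interscope device without adjunctive modality". There is no resection qualifier.
- **Populations (8.2).** Intent to Treat covers subjects "either treated with the EndoRotor alone or with another adjunctive modality". Per Protocol requires "complete lesion resection with the EndoRotor alone without any adjunctive modality resection".
- **Procedure (5.7).** Lesions "will be attempted to be removed entirely with the EndoRotor® with no other treatment modalities". The same bullet then allows conversion to a different resection modality if completion with the EndoRotor is not feasible.

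The one rule on classifying APC is in 5.7: APC or a similar technique used for hemostasis on a resected lesion does not count as an alternative resection modality. Nothing is said about APC aimed at lesion tissue. Sections 1.2.1 and 1.3.1 describe APC and thermal techniques as ablative and contrast them with resection that yields a specimen.

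**The concern.** Consider a subject whose visible lesion is completely resected with the EndoRotor, whose base or margin is then deliberately ablated as treatment, and who has no definitely or probably device-related serious adverse event. On its literal wording, 4.1 makes this subject a Technical Success, because ablation is not another resection modality. The 8.4 population sentence leaves the same subject out, because an adjunctive modality was used. Two analysts following the plan could build different numerators and denominators for the primary result.

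Both readings favor the device. One credits a combination-treated subject to the EndoRotor and the other removes the subject. No section explicitly scores the subject as a non-success. If such subjects are kept, they also enter the 90-day persistence result, which 8.4 names as a quantity for analysis and 4.2 lists as a secondary endpoint. Any benefit of the ablation would then be read as a benefit of the EndoRotor.

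The gap may be hard to close afterwards. The index-procedure data list in 5.7.1 has no item for use of another modality or its purpose. Section 5.7 and Appendix 1 also allow a second procedure, and the word concomitant does not settle whether a modality used then would count.

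**Working it through.** **Step 1: classify one subject under each text.** The subject has full EndoRotor resection, then ablation that is not for hemostasis, and no device-related SAE.

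| Text | Disqualifying modality | Result |
|---|---|---|
| Synopsis, 4.1, endpoint restated in 8.4 | another resection modality | success |
| 8.4 population sentence | any adjunctive modality | outside the set |
| 8.2 Per Protocol | the EndoRotor-alone condition points to wide scope; the word resection after modality points to narrow scope | unclear, more naturally outside |
| 5.7 hemostasis rule | covers hemostatic APC only | not settled |

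The clear conflict is between 4.1 and the 8.4 population sentence, and so also within 8.4. If the ablation treated residual lesion, the complete-resection condition in 8.2 excludes the subject on any reading.

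**Step 2: the plan's own precision figure.** Section 8.8 assumes n = 60 and a success rate of 0.85, so x = 0.85 × 60 = 51. The Clopper-Pearson limits are the 0.025 quantile of Beta(x, n − x + 1) and the 0.975 quantile of Beta(x + 1, n − x). For 51/60 they are 0.734 and 0.929, with half-width 0.0974. This agrees with the stated 0.0972 to within 0.0002. The stated limits, 0.782 to 0.967, are not reproduced (they match 45/50). That is a separate matter and does not affect this point.

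**Step 3: effect of the classification.** Assumptions: one lesion per subject; 51/60 successes when every ablated subject is counted as a success; k of those 51 were ablated; excluded subjects are not replaced. The documents give no value for k, so a range of 1 to 9 is shown (1.7% to 15% of 60).

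- Counted as success: 51/60 = 85.0% for every k
- Excluded: (51 − k)/(60 − k)
- Counted as non-success: (51 − k)/60

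| k | Excluded (exact 95% CI; half-width) | Non-success (exact 95% CI; half-width) |
|---|---|---|
| 1 | 50/59 = 84.7% (0.730–0.928; 0.099) | 50/60 = 83.3% (0.715–0.917; 0.101) |
| 3 | 48/57 = 84.2% (0.721–0.925; 0.102) | 48/60 = 80.0% (0.677–0.892; 0.108) |
| 6 | 45/54 = 83.3% (0.707–0.921; 0.107) | 45/60 = 75.0% (0.621–0.853; 0.116) |
| 9 | 42/51 = 82.4% (0.691–0.916; 0.112) | 42/60 = 70.0% (0.568–0.812; 0.122) |

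Moving from success to exclusion lowers the estimate by 0.3 points (k = 1) to 2.6 points (k = 9). Moving from success to non-success lowers it by 1.7 to 15 points. Under exclusion the half-width is on the edge of the 0.10 target in 8.8 at k = 2 (49/58, half-width 0.1004) and above it from k = 3.

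**The case against.** The strongest reply is that 4.1 defines an outcome while 8.2 and 8.4 define a population, so meeting one and falling outside the other is not in itself a contradiction. A subject with an eligibility deviation can do the same. Section 8.4 also says that it uses the Per Protocol population, so its sentence may be only a paraphrase of 8.2. In addition, an exemption limited to hemostasis suggests that APC aimed at lesion tissue does count as another modality, which would make the subject a failure under 4.1.

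Much of this stands, and it limits the point. A reader might infer any of the following, and the documents do not support them:

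- **That 8.2 keeps the ablated subject in Per Protocol, against 8.4.** The EndoRotor-alone condition, and the contrast in the Intent to Treat definition, more naturally agree with 8.4.
- **That 5.7 bars other modalities.** It states what will be attempted and intended, then allows conversion. It is not a scoring rule.
- **That the conflict itself could move the success rate from 100% to 80%.** That would need ablated subjects to be scored as failures, which no section explicitly does. If all other subjects succeed, success versus exclusion gives 100% either way: 60/60 has an exact lower limit of 0.940, and 48/48 has 0.926.
- **That ablation will be common in this trial.** The statement in 5.7.1 that "they often are treated with avulsion or Argon Plasma Coagulation" describes usual care for recurrent lesions, not ablation added to the EndoRotor.
- **That persistence is understated by a known amount.** That would need both an ablation rate and an ablation effect, and the documents give neither.

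The reply does not remove the core. The hemostasis rule supports failure only by inference, and the literal endpoint wording points the other way.

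**Conclusion.** The point holds for one type of subject: full EndoRotor resection followed by ablation that is not for hemostasis. The endpoint wording makes this subject a success, the 8.4 analysis set omits the subject, and nothing beyond an inference from the hemostasis rule counts the subject against the device.

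The size is conditional. With 51/60 successes and 1 to 9 ablated subjects among them, the choice between the two readings that the text offers is worth 0.3 to 2.6 points. The difference between crediting these subjects and scoring them as non-successes is 1.7 to 15 points. If no subject is ablated with treatment intent, the effect is nil. The ambiguity sits in the primary endpoint and costs little to remove before data are seen, so it should be corrected. It is distinct from the wider issue that the Per Protocol set selects on part of the endpoint it is used to estimate.

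**What to change.** 1. Use one analysis definition of a disqualifying modality in the synopsis, 4.1, 8.2 and 8.4: any other modality used to remove or destroy lesion tissue at any session. Keep the existing hemostasis exemption explicit, and state that it applies to the population definition as well as to the endpoint.
2. Score subjects who received such a modality as Technical Success non-successes, with all treated subjects (the 8.2 Intent to Treat population) as denominator. Report their 90-day persistence separately.
3. Record on the procedure CRF, for each session, any other modality used and its purpose.
4. In 5.7, reconcile the treatment-modality and resection-modality wording. The definition in item 1 only classifies subjects for analysis; it neither adds nor changes a procedural rule.

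The cost is protocol and SAP wording plus a small CRF addition. Item 2 goes beyond wording, because it changes the denominator for Technical Success from Per Protocol to all treated subjects. The reported success rate may be lower as a result.
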